10.4. FOOD ALLERGEN EXPOSURE

The occurrence of a safety event associated with accidental food allergen ingestion will be reported as a food allergen exposure. Any such event that meets the definition of an SAE will also be reported as an adverse event. All reported food allergen exposures will be listed by age group, group/cohort, and subject.

The number of subjects experiencing any food allergen exposure, the number of subjects experiencing a food allergen exposure in response to peanut (or nonpeanut), the number of exposures of each (peanut-related and nonpeanut related) experienced per subject, and the total number of food allergen exposures (peanut and nonpeanut related) will be summarized. The number of exposures considered SAEs, those that required treatment, and those that required epinephrine use will also be summarized.

10.5. SYMPTOMS DURING DOSING

During study product dosing, the severity of pre-specified allergy symptoms is rated as mild, moderate, severe, life-threatening, or death according to the CoFAR severity grading scale. In addition, the presence of dose-related allergy symptoms is recorded for each dose.

The number of subjects experiencing any dose-related allergy symptoms during study product dosing at the study site and the maximum severity of symptoms will be summarized at each dose level for each cohort. For Group 1, this will include all dose levels included in initial dose escalation, up-dosing, and 300 mg QD maintenance and extended maintenance dose. For Group 2, subjects are expected to dose at the 300 mg level, but dose reductions may occur. Any doses other than 300 mg for Group 2 will be summarized, but this data is expected to be sparse. Dosing at the study site and at-home dosing will be summarized separately.

If a subject is administered the same dose at more than 1 study site visit (eg, dose was the same as the previous visit or dose was increased with a subsequent dose reduction), the most severe symptoms will be summarized for that dose level.

Sponsor: Aimmune Therapeutics, Inc.

Protocol: ARC0004

Version: Version 1.0, 10Jul2019

10.6. SYMPTOMS DURING DBPCFC

During each food challenge, the severity of pre-specified symptoms is rated on the CoFAR scale as mild, moderate, severe, life-threatening, or death at each dose level of each food product. In addition, the presence of any dose related symptoms is identified.

The number of subjects experiencing any dose related symptoms and the maximum severity of any symptoms will be summarized by individual dose level and overall during the Screening peanut challenge, Maintenance peanut challenge (Group 1 only) and the Exit peanut challenge by group/cohort. Subjects will be counted at most once per type of challenge and dose level for symptom severity at the most severe level recorded for that subject.

Symptoms at the maintenance and Exit DBPCFCs will be listed by age group, group/cohort, and subject.

10.7. PREGNANCY TEST RESULTS

Pregnancy test results will be listed by age group, group/cohort, subject and visit.

10.8. SPIROMETRY AND PEF

Spirometry and/or Peak Expiratory Flow (PEF) assessments are performed at screening, initial dose escalation, and prior to any DBPCFC. PEF is also performed at each Up-dosing, maintenance, and extended maintenance visit. Spirometry may be performed at any time during the study where a subject's pulmonary status is in question. Three attempts of PEF are performed and the best (highest) value flagged in data listings. Only the best PEF value will be summarized.

Observed values for PEF, forced expiratory volume in one second (FEV₁), FEV₁ percent predicted, FEV₁/FVC ratio where FVC is forced vital capacity, and FEV₁/FVC percent predicted as well as changes from baseline will be summarized at each applicable visit and by group/cohort. Group 1 will be summarized separately for up-dosing and maintenance. The extended Maintenance summary will include Group 1, Group 2 Cohort 1, Group 2 Cohort 2, Group 2 Cohort 3A, Group 2 Cohort 3B, and Group 2 Cohort 3C.

Results will be listed by age group, group/cohort, subject, and visit.

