6.3.9 Follow-up Extended Maintenance Visits

The follow-up EM period visits should take place approximately every 14 weeks and occur on a day when the dosing interval is due to be changed and/or the subject is due to take the previously specified dose.

Subjects should withhold their daily home dose of study product on in-clinic dosing days, but should take all other prescribed medications as scheduled.

Some or all of the following assessments/procedures are scheduled for in-clinic dosing EM period visits in the CRC, according to the Schedule of Events:

- Concomitant medication review.
- Diet (food allergen exposure) history update.
- Return unused sachets or capsules to the clinic at each visit.
- Symptom-directed physical examination.
- Pre-dose vital sign measurement (BP, PR, body temperature).
- Peak expiratory flow rate (PEFR), performed in all subjects 6 years of age or older, measured at approximately the same time for each assessment visit. Three attempts of PEFR should be performed, and the best attempt selected. For subjects 4 or 5 years of age: peak flow rates are to be attempted, but reliable performance is not required for the subject to enter the study or undergo study procedures at the investigating physician's discretion. The attempt must be documented, and a clinical assessment is required.

- Spirometry* (FEV₁), performed when PEFR shows a clinically relevant reduction or the subject shows clinical deterioration (e.g., active wheeze on physical examination); 3 attempts of FEV₁ should be performed, and the best attempt selected.
*Only for subjects 6 years of age and older who are able to adequately perform spirometry. In order to assess whether the subject is able to adequately perform spirometry, the spirometry must be attempted, and any attempt must be documented.
- Assessment of asthma control in asthmatic subjects using the Asthma Control Test questionnaire.
- Urine pregnancy test.
- Skin prick test at entry into EM and every 28 weeks while on QD treatment; more frequently when on nondaily treatments as per the Schedules of Events ([Appendix 1](#)).
- Blood draw to collect samples for:
 - Immunoglobulin assays. The amount of blood taken for the immunoglobulin assays will be communicated from the central laboratory and included in the Manual of Procedures.
 - CBC, obtained with the same venipuncture as the blood draw for the immunoglobulin assays.

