- h) PEFR to be performed in all subjects 6 years of age or older, measured at approximately the same time for each assessment visit; 3 attempts of PEFR should be performed, and the best attempt selected. For subjects 4 or 5 years of age, PEFR is to be attempted, but reliable performance is not required for the subject to enter the study or undergo study procedures at the investigating physician's discretion. The attempt must be documented, and a clinical assessment is required. Spirometry (FEV₁) is to be performed in subjects 6 years of age or older when PEFR shows a clinically relevant reduction or the subject shows clinical deterioration (e.g., active wheeze on physical examination.); 3 attempts of FEV₁ should be performed, and the best attempt selected. In order to assess whether the subject is able to adequately perform spirometry, the spirometry must be attempted, and any attempt must be documented.
- i) For females of childbearing potential.
- j) FAQLQ and FAIM questionnaires to be filled out after ARC003 Exit DBPCFC and after ARC004 Exit DBPCFC.
- k) TSQM-9 and Exit questionnaires to be answered after Exit DBPCFC.
- l) Blood for peanut-specific IgE, IgG4 is to be drawn prior to DBPCFC.
- m) Optional blood draw at selected centers according to local institutional guidelines for minimal risk phlebotomy procedures in children. No more than 50 mL total within 8 weeks may be drawn.
- n) Blood draw to be collected prior to the Exit DBPCFC.
- o) Subjects withdrawing early from ARC004 with GI symptoms who were not already enrolled in the optional saliva sub-study will be allowed to enroll upon early termination.
- p) The first 2 twice weekly (BIW), once weekly (QW), and every other week (QOW) doses (as applicable) administered to Group 1 during the Extended Maintenance Period will be in clinic.
- q) Post-Maintenance DBPCFC to 2000 mg (4043 cumulative) peanut protein is performed only at the end of the 24 week 300 mg Maintenance Period (not at each CRC dosing visit).
- r) DBPCFC to 2000 mg (4043 mg cumulative) peanut protein at Exit visit only.
- s) AEs will be evaluated from the onset until the event is resolved or medically stable, or until 30 days after the Early Discontinuation Visit, whichever comes first. GI AEIs will be monitored according to [Section 7.3.3.2](#).
- t) Telephone follow-up will occur 1 day after each escalation visit and Initial Maintenance visit to inquire about allergic symptoms and promote compliance.

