6. GENERAL ASPECTS FOR STATISTICAL ANALYSIS

6.1. STATISTICAL NOTATION AND METHODOLOGY

Unless stated otherwise, the term “descriptive statistics” refers to the number of subjects (n), mean, median, standard deviation, minimum, and maximum for continuous variables and frequencies and percentages for categorical variables.

Unless specified otherwise, the denominator for percentages for categorical data will be based on the number of subjects or observations with non-missing data appropriate for summary purposes. The denominator for percentages for incidence data (such as adverse events) will be based on the number of subjects in the analysis population “at risk”. Select ordinal data may be summarized using both descriptive statistics and counts and percentages of subjects in each category, as appropriate.

Minimum and maximum values will be presented at the precision of the original value, means, medians will be rounded to 1 decimal place greater than the precision of the original value, standard deviations and standard errors will be rounded to 2 decimal places greater than the precision of the original value. Percentages will be rounded to 1 decimal place. Percentages that round down to 0 or up to 100% will be displayed as “<0.1%” and “>99.9%”, respectively. Other statistics (e.g., confidence intervals (CIs)) will be presented using the same general rules outlined above, or assessed for the most appropriate presentation based on the underlying data.

Unless otherwise noted, values reported as greater than or less than some quantifiable limit (e.g., “< 1.0”) will be summarized with the sign suppressed in summary tables and figures, using the numeric value reported. Data will display on subject listings to include the sign.

Summary tables will be presented by group/cohort displayed as Group 1 and Group 2 with Cohort 1, Cohort 2, Cohort 3A, Cohort 3B, and Cohort 3C. For disposition, demographic, and other summaries of baseline and history data, a Total column for both groups combined will be included. For any summaries of events such as adverse events or concomitant medications, event incidences will be summarized in the Safety population separately for the following group/cohort study periods:

- Group 1: IDE and Up-Dosing, all QD Maintenance (including extended maintenance), Overall
- Group 2 Cohort 2: QOD, BIW, and Overall
- Group 2 Cohort 1 (includes QD only)
- Group 2 Cohort 3A (includes QD only)

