7.5. DATA DERIVATIONS AND DEFINITIONS

The following definitions and derivations will be used throughout this study:

- Study day is calculated relative to the first dose date in ARC004 as (assessment date – first dose date + 1) for assessments and visits performed on or after the first dose date, and (assessment date – first dose date) for assessments and visits prior to the first dose date.
- In this follow on study, baseline is defined as the last non-missing value prior to the first dose of study treatment in the study where study product is first received. For Group 1 patients (those previously on placebo in ARC003), baseline is relative to first dose of AR101 in study ARC004. For Group 2 patients (those continuing on AR101 therapy from ARC003), baseline is relative to first dose of AR101 in study ARC003. If no ARC004 data were entered for a Group 1 subject, use the last available ARC003 data prior to first dose of AR101 in ARC004. For food challenge end points, the ARC003 exit food challenge will serve as the baseline for both groups.

Sponsor: Aimmune Therapeutics, Inc.

Protocol: ARC0004

Version: Version 1.0, 10Jul2019

- Change from baseline is calculated as observed value after the first dose – baseline value.
- Group 1 Initial Dose Escalation period is defined as the time period beginning with the date and time of the first dose of study product in clinic and ending with the date of the last dose of study product taken prior to Up-dosing.
- Group 1 Up-dosing period is defined as the time period beginning with the date and time of the first home dose of study product at 3 mg, and ending with the date and time of first in-clinic dose at 300 mg. This period will be, ideally, 22 weeks in duration, but may be extended to a maximum of 40 weeks to accommodate dose reductions and re-escalations, if necessary.
- Group 1 Maintenance period is defined as the time period beginning with the date and time of the first home dose of study product at 300 mg and ending with the date of the last dose of study product taken prior to the maintenance DBPCFC. The maintenance period lasts approximately 24 weeks.

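### SAP 10.8 tabulates mean FEV1 and change from baseline by visit and cohort, but FEV1 is measured only on signs of worsening, so these means do not represent the cohorts

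*SAP*

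**What the plan says.** **Collection.** Peak flow is taken at each ARC004 visit type in subjects aged 6 years or older. FEV1 is conditional. In Protocol 6.3.9 it is "performed when PEFR shows a clinically relevant reduction or the subject shows clinical deterioration". The same condition stands in Protocol 6.2 (screening), 6.3.1 and 6.3.2 (initial escalation), 6.3.3.1 (up-dosing), 6.3.5 and 6.3.6 (maintenance), 6.3.8.1 (start of a new interval) and 6.3.10 (exit). The Appendix 1 footnotes repeat it: spirometry "is to be performed in subjects 6 years of age or older when PEFR shows a clinically relevant reduction" or on clinical deterioration.

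**Description in the SAP.** SAP 10.8 says "Spirometry and/or Peak Expiratory Flow (PEF) assessments are performed at screening, initial dose escalation, and prior to any DBPCFC", and adds "Spirometry may be performed at any time during the study where a subject's pulmonary status is in question".

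**Summary.** The same section lists observed PEF, FEV1, FEV1 percent predicted, FEV1/FVC and FEV1/FVC "percent predicted as well as changes from baseline will be summarized at each applicable visit and by group/cohort". By SAP 6.1 the default for such data "refers to the number of subjects (n), mean, median, standard deviation, minimum, and maximum for continuous variables".

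**Baseline.** In SAP 7.5, "baseline is defined as the last non-missing value prior to the first dose of study treatment in the study where study product is first received". That is ARC003 for Group 2 and ARC004 for Group 1. A Group 1 subject without ARC004 data is to "use the last available ARC003 data prior to first dose of AR101 in ARC004".

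**Other handling.** SAP 7.2 leaves unscheduled visits out of by-visit summaries, and SAP 7.6 provides no imputation for FEV1. SAP 10.8 plans neither a count of subjects who had spirometry nor a note on why it was done.

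**The concern.** A by-visit mean is normally read as the state of the cohort at that visit. Here a subject with stable peak flow and no deterioration has no FEV1 scheduled, so a cell holds mainly those who gave cause for a test. The mean and the change from baseline then describe that subset.

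The study exists to describe safety by dosing interval, and these means will stand side by side by group and cohort. A reader could take a fall in one column as lung-function loss on that regimen. A reader could also compare two columns that differ only in how readily the test was triggered. The informative quantity, how many subjects needed spirometry, is not tabulated.

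**Working it through.** The plan states no FEV1 figure (expected number tested, SD, trigger size or change), so there is nothing of its own to reproduce. The check sets the collection rule against the summary rule and then sizes the selection effect under stated assumptions.

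**1. Rule against rule.** Collection is conditional on worsening at every ARC004 visit type. The summary has no condition, no restriction and no caveat. The selection follows from these two texts and needs no assumption.

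**2. Size with a routine baseline.** Assume that the true mean change in FEV1 percent predicted is 0, with SD *s*. Its correlation with the peak-flow change is *r*, and the worst share *q* by peak flow is tested. Then

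E[change | tested] = -*r* x *s* x φ(z_q)/*q*,

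where z_q cuts off the tail *q* of a standard normal and φ is its density. The values of φ(z_q)/*q* are 2.063 (q = 0.05), 1.755 (q = 0.10) and 1.400 (q = 0.20).

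- q = 0.10, r = 0.6, s = 8: -0.6 x 8 x 1.755 = -8.4 points
- q = 0.20, r = 0.4, s = 8: -0.4 x 8 x 1.400 = -4.5 points
- q = 0.05, r = 0.8, s = 8: -0.8 x 8 x 2.063 = -13.2 points

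**3. Cross-check with an explicit threshold.** This simulation assumes an SD of 12% for peak-flow change, true mean FEV1 change 0, r from 0.3 to 0.7 and s from 8 to 12.

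- Trigger at a 10% fall: about 20% tested, mean change -3.3 to -11.8 points
- Trigger at a 20% fall: about 5% tested, mean change -5.0 to -17.5 points
- With r = 0 the effect is 0

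**4. Comparability.** Take two cohorts with the same true change (0), s = 8 and r = 0.6, where one has 5% tested and the other 20%. Their expected means are -0.6 x 8 x 2.063 = -9.9 and -0.6 x 8 x 1.400 = -6.7 points. They differ by 3.2 points although nothing differs in truth, and the cohort tested less often looks worse. The protocol gives no numeric threshold for a relevant fall in peak flow.

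**5. Triggered baseline.** ARC004 screening and initial escalation carry the same trigger, so a Group 1 baseline FEV1 may come from a subject already below his or her norm. In the simulation with a 10% trigger at both times, the mean change among those tested twice was -0.02 to +0.3 points, which is essentially zero. At a 20% trigger only about 0.01% were tested twice, too few to inform. By the planned sizes in Protocol 7.8.3, Group 1 is 130 of 130 + 120 + 50 + 175 = 475 subjects, or 27%.

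**6. Growth.** SAP 10 summarises safety mainly for ages 4 to 17. For Group 2 the time from baseline to exit runs from (22 + 24 + 28)/52 = 1.4 years to (40 + 24 + 84)/52 = 2.8 years by the planned periods. With assumed growth *g* in absolute FEV1 and selection effect *b*, the net change over *y* years is (1 + g)^y x (1 + b) - 1.

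- y = 1.5: g = 5%, b = -12% gives -5.3%; g = 8%, b = -4% gives +7.7%
- y = 2.5: g = 5%, b = -12% gives -0.6%; g = 8%, b = -4% gives +16.4%

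So absolute FEV1 may rise or fall in the table.

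**The case against.** A reader might infer that the table is bound to show a false decline, with the sign fixed by the trigger. The documents do not support that.

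- A Group 1 baseline may itself be triggered, and the Group 2 baseline comes from ARC003, whose spirometry schedule is not in these documents. The FEV1 exclusion in Protocol Appendix 7 suggests spirometry at ARC003 entry but does not prove it.
- Growth can outweigh the effect in absolute FEV1.
- A fall in the tested subjects is real for them. It misleads only when read as the cohort's change.

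A reader might also infer that cohorts do differ in how often they are tested. Nothing in the documents shows this, so non-comparability is conditional on it.

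The best defence of the plan has four further parts.

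- *The SAP knows that spirometry is symptom-driven, and it speaks of applicable visits.* True, but no restriction or caveat reaches the table. The and/or in its first sentence is met by PEF alone. The protocol's requirement that spirometry be attempted concerns ability to perform the conditional test. If some sites tested routinely, cells would mix routine and triggered values that the table cannot separate.
- *Existing safeguards.* Each cell shows n, PEF is summarised alongside, listings are planned, and SAP 10.11 has asthma-control shift tables. These help, but n alone does not say out of how many or why.
- *Triggered tests at unscheduled visits stay out of the means.* This reduces the selection in the by-visit cells, but it also drops for-cause tests from the only FEV1 tables. Subjects must also be free of active wheezing before escalation doses, so those Group 1 cells may hold few values.
- *Limited importance.* Spirometry is neither the primary nor a named secondary endpoint, and no formal comparison is planned. This stands and bounds the harm.

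**Conclusion.** The FEV1 and FEV1/FVC part of SAP 10.8 is wrong as written. Followed exactly, it yields by-visit means from subjects selected for worsening, which do not represent the cohort and are not comparable between cohorts if trigger rates differ. That conclusion rests on the text alone.

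The size rests on assumptions. For percent predicted with a routinely measured baseline, an apparent decline is likely, roughly 4 to 13 points at SD 8, correlation 0.4 to 0.8 and 5% to 20% tested. The simulation, which also allows SD 12 and other correlations, widens this to 3.3 to 17.5. The direction is not assured for Group 1 or for absolute FEV1. The consequence is confined to interpretation of a supportive safety table, and the change is a cheap improvement.

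**What to change.** In SAP 10.8:

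1. Restrict by-visit means and changes from baseline to PEF.
2. For spirometry, report by group/cohort and regimen period the number and percent of subjects with at least one post-baseline test, counting unscheduled visits. The denominator is subjects at risk in that period aged 6 years or older; state whether age is taken at ARC004 consent, as in SAP 8.3, or at the visit.
3. Report each subject's worst FEV1 percent predicted in categories over the same denominator, with an explicit not-tested category. The 60% and 80% cut-points in Protocol Appendix 2 could serve. State where subjects who could not perform the test are counted.
4. Keep the listings already planned.
5. Add a footnote that spirometry was done only on trigger. Tabulate the reason for testing only if it was collected; the documents do not show that the CRF records it.

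The cost is SAP wording and one table shell, using values already collected. The downside is that mean FEV1 by visit is no longer tabulated.

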10.9. VITAL SIGNS

BMI will be calculated as (weight in kilograms) / (height in meters)².

Vital signs (pulse rate, systolic/diastolic blood pressure, body temperature, height, BMI and weight) will be listed by age group, group/cohort, subject and visit. Observed values and change from baseline will be summarized by group/cohort at each scheduled visit and

Sponsor: Aimmune Therapeutics, Inc.

Protocol: ARC0004

Version: Version 1.0, 10Jul2019

time point for pulse rate, systolic/diastolic blood pressure, and body temperature. At DBPCFC vital signs are scheduled to be taken just prior to each dose given. At Initial Dose Escalation, Up-dosing, and Maintenance visits, and EM visits, vital signs are to be taken pre-dose and after each dose given. If multiple measurements are recorded pre-dose or post-dose at a given in-clinic visit, the last pre-dose measurement and the first post-dose measurement will be used in the summaries.

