- Post-dose vital sign measurements (BP, PR) within 15 to 30 minutes post-dose, and prior to next dose, and at 30-minute intervals thereafter, if the time between doses is extended, and for the duration of the post-dose observation period.
- Monitoring for AEs, including allergic symptoms (see below and [Section 6.5.3.1](#) and [Section 7.2](#)).
- Subjects will be reminded to continue to follow a peanut-avoidant diet for the duration of the study.

Subjects may have clear liquids or flavored gelatin (eg, Jell-O[®]) during the day of the initial day escalation procedure while they are being given the desensitization doses. At a minimum, subjects must be observed for 90 minutes (1½ hours) after completion of dose escalation, with vital sign measurements and assessment for signs and symptoms of allergic reaction performed every 30 minutes. Any signs or symptoms of allergic reaction will be recorded in the case report form (CRF) on the appropriate Dosing Symptom/AE form.

If Day 1 dose escalation is completed with no symptoms detected after 1½ hours of post-dose observation following the last dose, the subject may be sent home from the CRC. If the subject exhibited mild symptoms, the duration of the observation period should be a minimum of 1 hour after resolution of the symptoms. For moderate symptoms, the observation period should be extended to a minimum of 2 hours after resolution of the symptoms. And for severe symptoms, the subject should be observed for a minimum of 3 hours after resolution of the symptoms, either at the CRC or an emergency facility, as appropriate.

Any subject deemed to have severe symptoms that include hypoxia, hypotension, or change in mental status, stage 3 anaphylaxis defined in [Appendix 3](#), or who receives intensive therapy (to be determined by the investigator, but may include such interventions as IV epinephrine, intubation, or admission to an intensive care unit) for an allergic reaction at any time should be discussed with the Medical Monitor and discontinued from the study.

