*Only for subjects 6 years of age and older who are able to adequately perform spirometry. In order to assess whether the subject is able to adequately perform spirometry, the spirometry must be attempted, and any attempt must be documented.

- Study product administration under observation in the clinic.
- Post-dose vital sign measurements (BP, PR) within 15 to 30 minutes post dose, prior to discharge, and at the investigator's discretion during the post-dose observation period.
- Take home capsules for daily dosing until next visit.
- Monitoring for compliance.
- Monitoring for AEs, including allergic symptoms ([Section 7.2](#)).
- Diary review with subject.
- Subjects will be reminded to continue to follow a peanut-avoidant diet for the duration of the study.
- Optional saliva collection at selected centers (per the Schedule of Events in [Appendix 6](#)).

At a minimum, subjects must be observed for 1½ hours after dose administration, with vital sign measurements and assessment for signs and symptoms of allergic reaction performed every 30 minutes. Any signs or symptoms of allergic reaction will be recorded in the CRF on the appropriate Dosing Symptom/AE form.

If up-dosing is completed with no symptoms detected after 1½ hours of post-dose observation, the subject may be sent home from the CRC. If the subject exhibited mild symptoms, the duration of the observation period should be a minimum of 1 hour after resolution of the symptoms. For moderate symptoms, the observation period should be extended to a minimum of 2 hours after resolution of the symptoms. And for severe symptoms, the subject should be observed for a minimum of 3 hours after resolution of the symptoms, either at the CRC or an emergency facility, as appropriate.

Any subject deemed to have severe symptoms that include hypoxia, hypotension, or change in mental status (stage 3 anaphylaxis defined in [Appendix 3](#)), or who receives intensive therapy (to be determined by the investigator, but may include such interventions as IV epinephrine, intubation, or admission to an intensive care unit) for an allergic reaction at any time should be discussed with the Medical Monitor and discontinued from the study.

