6.3.8 All Subjects (Groups 1 and 2): Extended Maintenance Visits

The EM period begins upon entry in ARC004 for Group 2, and following completion of the Post-Maintenance DBPCFC for Group 1.

6.3.8.1 Alternate Dosing Initiation Visit: Day 1

Subjects in Cohorts 2, 3B, and 3C will change to BIW dosing once they have tolerated QOD dosing for 4 weeks. Subsequently Cohort 3C may extend the interval further. Subjects extending their dosing interval (eg, QOD to BIW, BIW to QW, QW, to QOW) will do so by taking the first 2 doses of the new interval under observation in clinic (except QOD). Every effort should be made to ensure the new interval is the appropriate interval. Some or all of the following procedures may be performed at the first of these 2 visits, according to the procedures outlined in the Schedule of Events:

- Diet (food allergen) history.
- Concomitant medication update.
- Symptom-directed physical examination.
- Pre-dose vital sign measurement (BP, PR, body temperature).
- Peak expiratory flow rate (PEFR), performed in all subjects 6 years of age or older, measured at approximately the same time for each assessment visit. Three attempts of PEFR should be performed, and the best attempt selected. For subjects 4 or 5 years of age: peak flow rates are to be attempted, but reliable performance is not required for the subject to enter the study or undergo study procedures at the investigating physician's discretion. The attempt must be documented, and a clinical assessment is required.
- Spirometry* (FEV₁), performed when PEFR shows a clinically relevant reduction or the subject shows clinical deterioration (e.g., active wheeze on physical examination); 3 attempts of FEV₁ should be performed, and the best attempt selected.

*Only for subjects 6 years of age and older who are able to adequately perform spirometry. In order to assess whether the subject is able to adequately perform spirometry, the spirometry must be attempted, and any attempt must be documented.

- Urine pregnancy test.
- Oral administration of AR101.
- Skin prick test.
- Post-dose vital sign measurements (BP, PR) within 15 to 30 minutes post dose, prior to discharge, and as indicated per investigator discretion during the post-dose observation period. Subjects with moderate or severe symptoms should be monitored every 30 minutes.
- Blood draw to collect samples for:

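### SAP 10.9 tabulates only the first post-dose vital signs of each visit, so its tables can miss a later blood-pressure fall, and it does not say how the rule works across the five doses of Initial Escalation Day 1

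*SAP*

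**What the plan says.** SAP 10.9 summarises observed values and change from baseline by group/cohort, at each scheduled visit and "time point for pulse rate, systolic/diastolic blood pressure, and body temperature". It does not define a time point. For dosing visits it gives the schedule as "vital signs are to be taken pre-dose and after each dose given". The selection rule is: "If multiple measurements are recorded pre-dose or post-dose at a given in-clinic visit", then "the last pre-dose measurement and the first post-dose measurement will be used in the summaries". Its stated unit is the visit, not the dose. No worst value and no count against a limit is planned for vital signs. All readings stay visible elsewhere, because vital signs "will be listed by age group, group/cohort, subject and visit".

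The protocol collects more than one post-dose reading:

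- **Initial Escalation Day 1 (6.3.1):** one pre-dose item, then readings labelled post-dose "within 15 to 30 minutes post-dose, and prior to next dose, and at 30-minute intervals thereafter". The 30-minute repeats apply if the gap between doses is extended, and throughout the observation after the last dose. That observation lasts at least 90 minutes.
- **Day 2 and up-dosing visits (6.3.2, 6.3.3.1):** at least 90 minutes of observation, "with vital sign measurements and assessment for signs and symptoms of allergic reaction performed every 30 minutes".
- **Alternate dosing initiation visits (6.3.8.1):** a reading 15 to 30 minutes after the dose and one before discharge, with more at the investigator's discretion. "Subjects with moderate or severe symptoms should be monitored every 30 minutes".
- **Maintenance and Extended Maintenance visits (6.3.6, 6.3.9):** a reading at 15 to 30 minutes, with more only if observation runs past 30 minutes.

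**The concern.** The readings that the rule leaves out of the tables are not a random subset. At Maintenance, Extended Maintenance and initiation visits an uneventful dose generates few extra readings, while a reaction generates many. A table built only on the first reading therefore leans towards showing no effect.

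Blood pressure matters in this study. Under protocol Appendix 3, reduced blood pressure within minutes to hours of allergen exposure is by itself a criterion for suspecting anaphylaxis, with numeric limits. SAP 10.9 never sets the measurements against those limits. Change scores do not fill the gap: SAP 7.5 takes baseline before the first AR101 dose, which for Group 2 lies in ARC003, and no change from the same visit's pre-dose value is planned.

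What is at stake is a planned safety table that could look clean although later readings at the same visits did not.

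**Working it through.** The plan gives no figure of its own to reproduce here, apart from the Day 1 cumulative dose. Table 1 of the protocol checks: 0.5 + 1 + 1.5 + 3 + 6 = 12 mg.

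**Up-dosing visit.** Inputs from protocol 6.3.3.1: first reading at 15 to 30 minutes, readings every 30 minutes, minimum observation 90 minutes.

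- Readings at about 30, 60 and 90 minutes give 3.
- The SAP rule keeps 1, so 3 − 1 = 2 of 3 are not tabulated.
- Observation time after the kept reading: 90 − 30 = 60 minutes to 90 − 15 = 75 minutes.

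**Initial Escalation Day 1, all five doses given, no symptoms.** Inputs from protocol 6.3.1: doses 20 to 30 minutes apart, a reading after each dose and before the next, then every 30 minutes for 90 minutes after the last dose.

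- Last dose: 4 × 20 = 80 minutes to 4 × 30 = 120 minutes after the first.
- End of visit: 80 + 90 = 170 to 120 + 90 = 210 minutes.
- Post-dose readings: 4 between doses + 3 after the last dose = at least 7.

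The SAP allows two readings of its rule:

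1. *Per visit, with the protocol's labels.* The pre-dose value is the one before 0.5 mg and the first post-dose value follows 0.5 mg. The order is correct, but the tabulated value reflects 0.5/12 = 4% of the cumulative dose, and 7 − 1 = 6 of at least 7 post-dose readings are not tabulated.
2. *Per dose, taking each dose as a time point.* One post-dose reading is kept for each of five doses. That leaves 7 − 5 = 2 untabulated, the ones at about 60 and 90 minutes after the 6 mg dose, together with any repeats taken because a gap between doses was extended.

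**Maintenance or Extended Maintenance visit, dose tolerated, 30-minute observation.** The required timing may give a single post-dose reading, so nothing need be lost. The loss arises when observation is prolonged.

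**The case against.** The strongest reply is that a clinically significant fall should be reported by another route. Clinically significant hypotension is a severe symptom (protocol 6.5.1), and any change that the investigator judges clinically significant is an adverse event (7.3.1). The adverse event tables include in-clinic dosing symptoms (SAP 10.3), dosing symptoms are tabulated by dose level and maximum severity (10.5), and anaphylactic reactions by severity and individual symptom (10.14). This stands, and it narrows the gap to falls that were measured but not reported. Those routes depend on investigator judgement in an open-label study, so a table of the measurements remains a useful check.

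A second reply is that the first reading falls in a fixed 15 to 30 minute window and is comparable across subjects, while a worst-of-several value partly reflects how many readings were taken. That also stands, and is why the first post-dose row should stay.

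Third, the larger losses concern Group 1 only: 130 of the planned 130 + 120 + 50 + 175 = 475 subjects (protocol 7.8.3). The 345 in Group 2 lose readings mainly when observation is prolonged. Vital signs are not a listed endpoint and no formal comparison is planned.

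A reader might also infer that the Day 1 pair is in reverse time order. If between-dose readings were called pre-dose for the next dose and the rule were applied per visit, the last pre-dose value would fall at 75 to 120 minutes, some 60 to 105 minutes after the first post-dose value. The documents do not support that labelling: protocol 6.3.1 lists one pre-dose measurement and calls the later ones post-dose, and SAP 10.9 follows the same structure.

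**Conclusion.** The point holds as a limitation of the vital-sign tables. Post-dose readings after the first are left out, about 2 of 3 at an up-dosing visit. On Day 1, 6 of at least 7 are left out if the rule is read per visit, and at least 2 of 7 if it is read per dose. The omitted readings at Maintenance, Extended Maintenance and initiation visits come disproportionately from reacting subjects. The counts assume that readings are taken at the protocol's minimum frequency and that all five Day 1 doses are given.

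Four further inferences go too far:

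- The readings are not discarded; SAP 10.9 lists them all.
- Hypotension is not confined to listings, because reported events reach the adverse event, dosing-symptom and anaphylaxis tables.
- Vital signs are not the only objective measure of dosing reactions; peak flow, spirometry, observable signs and epinephrine counts are others.
- The tables can show an acute effect of the first supervised twice-weekly doses at 15 to 30 minutes, by comparing the pre-dose and post-dose rows of that visit. Only later shifts escape them.

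The primary endpoint, treatment-related adverse events, is not affected.

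**What to change.** Amend the selection rule in SAP 10.9 as follows:

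- At each in-clinic dosing visit, the pre-dose value is the last reading before the first dose of that visit.
- On Initial Escalation Day 1, each dose defines its own post-dose time point.
- Keep the first post-dose row as planned.
- Add a row for the worst post-dose value of the visit: lowest systolic and diastolic blood pressure, highest pulse rate.
- For that row, summarise change from the same visit's pre-dose value.
- Count the subjects who meet the reduced-blood-pressure limits already in protocol Appendix 3, stating which value the percentage drop is measured from.

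The cost is one SAP paragraph and modest programming on data already collected. The drawback is that the worst value depends partly on the number of readings, so it should be read beside the first post-dose row and not in place of it.
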